Timeline: Months 1-3 will be used for training, start-up efforts and pilots. We expect to randomize about 7-8 participants into the study each month in months 4-42. This rate of recruitment is feasible because over 500 unique clients receive services each month at CTULA, with an estimated 15-20% meeting all inclusion criteria (and $<15\%$ are expected to meet exclusion criteria). Given the number of clients served throughout this agency, we plan to limit recruitment to one or two of the employment agency sites, but can expand to other sites if needed. Recruiting more quickly would necessitate more study staff due to the number of intervention visits, and this rate is consistent with our substance abuse treatment studies. With this enrollment rate, all intervention should be completed by month 47 and final follow-ups by month 55, leaving 5 months for analyses and report writing.

Data Analysis: An important issue preceding analyses is to identify baseline differences between groups despite random assignment. Group differences that may relate to outcomes (e.g., psychiatric diagnoses, occupational or medical status, drinking severity, services received) will be used as covariates or fixed factors in analyses. All randomized participants will be included using intent-to-treat analyses. Four primary outcomes are determined a priori: longest duration of negative samples (LDNS), % negative BrACs, % days worked for pay, and time to job attainment. The first three are continuous variables that can be transformed if needed. Drinking outcomes rely primarily on objective indices (BrACs), with subjective reports supplementing objective indices, such that one can be considered drinking if either index is positive. For LDNS, missing BrACs will be considered to break a string of negative samples. For % negative BrACs and % days working, missing data will be considered missing (not impacting the denominator) in one analysis, and positive/not working in another to consider the range of possibilities. ANOVAs (or ANCOVAs) will be conducted for drinking data and % days employed, evaluating both short-term (BL to month 3) and longer-term (throughout follow-up) efficacy. Time to job attainment will be evaluated with Cox survivor analyses, including covariates if needed.

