The design includes four treatment groups, allowing for examination of three main contrasts. Aim #1 is to evaluate whether reinforcing negative BrACs reduces drinking. Contrast weights of +1 will be assigned to Groups B and D and weights of -1 to Groups A and C to evaluate differences in LDNS and % negative BrACs in those assigned to interventions reinforcing negative BrACs vs those not. Aim #2 is to assess if reinforcing job-related activities reduces time to job attainment and increases % days working. Contrast weights of +1 will be assigned to Groups C and D and -1 to Groups A and B. Aim #3 is to examine if reinforcing both negative BrACs and job activities produces synergistic effects in terms of primary drinking and employment outcomes. To test this hypothesis, we will assign contrast weights of +2 to Group D, +1 to Groups B and C and -3 to Group A.

Power analyses. Our studies reinforcing drug abstinence find Cohen's d effect sizes of 0.5 to ≥ 1.0 for substance use outcomes ([name] et al., 2000, 2004, 2005abc, 2006b, 2007a, 2010b, 2011a, 2012abc), and our pilot trial using cell phone recorded BrACs yielded an effect size of $d=0.52$ for LDNS and $d=0.62$ for % negative BrACs ([name] & [name], 2013). Our study reinforcing job activities and abstinence (Drebing et al., 2007) had an effect size of 0.47 in terms of increasing job acquisition and 0.49 for abstinence. We conservatively powered this study to detect the smallest of these effect sizes. Using a Type I error rate of $\alpha=.05$, a Type II error rate of $\beta=.20$, and power=0.80 (Cohen, 1988), 62 participants are needed to detect

an effect size of $d=0.47$ between conditions reinforcing a target behavior and conditions not reinforcing that behavior.

We expect a smaller, but still clinically meaningful, effect size of $f=.22$ when comparing across reinforcer conditions. With power 0.80, 64 participants/group can detect $f=.22$ using the 3-group contrast in Aim 3 (Cohen, 1988). To accommodate for missing data, we will randomize 280 participants in total (70/group).

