Economic Evaluation. If primary aims are supported, we will conduct cost-effectiveness analyses.

These interventions can be costly, and not only must costs of reinforcers be included, but so must administration costs, which include staff time for managing and delivering reinforcers. Despite costs, these interventions may provide benefits to society in terms of increased productivity and reduced healthcare service utilization (hospitalizations, ER visits). This study will estimate costs of these reinforcement interventions and determine their net benefit in terms of improving both drinking and employment outcomes.

a. Comprehensive administrative costs of interventions will be quantified (Olmstead et al, 2007abc; Rosenheck et al, 1995; Sindelar et al. 2007ab), including costs of prizes, mileage for purchasing them, BrAC testing and management (personnel time to arrange and review videos, and cell phones costs in Groups B and D), and setting and verifying job-related activities (Groups C and D only). Costs related exclusively to data collection will not be included (i.e., cell phones and staff salary for collection and viewing BrAC videos when not reinforced in Groups A and C). Costs for usual employment and clinical services, and reimbursement for same when applicable, will be ascertained.

b. General healthcare costs will be estimated by multiplying service units used by average unit costs. In- and out-patient, day hospital, aftercare and emergency room services will be estimated from CT claims data, and nationally from the Market Scan database, which estimates service costs.

c. Societal costs will be obtained on productivity (days worked, earnings, and workdays affected by substance use), automobile crashes (including property damage, injuries, and fatalities), and criminal justice system costs. Participants receiving reinforcement interventions may have reduced societal costs, and the SU collects data on these variables, police contacts, court hearings, and incarceration, along with timing of events that resulted in criminal justice service use so acts occurring before study participation can be separated from those occurring during it in terms of resource utilization. Unit costs of services will be estimated from national reports (Pastore & Maguire, 2003; US Dept. of Justice 2006).

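### Aims 1 and 2 each rest on two unranked primary outcomes with no success rule, error control or deciding horizon, and the longer-term BrAC outcomes are not defined

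*Combined protocol and SAP*

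**What the plan says.** The Data Analysis section lists the primary outcomes: "Four primary outcomes are determined a priori: longest duration of negative samples (LDNS), % negative BrACs, % days worked for pay", and then time to job attainment. The contrasts paragraph tests Aim 1 on LDNS and % negative BrACs (Groups B and D against A and C). For Aim 2 (C and D against A and B) it says: "Aim #2 is to assess if reinforcing job-related activities reduces time to job attainment and increases % days working".

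The drinking outcomes and % days employed go into ANOVA or ANCOVA, "evaluating both short-term (BL to month 3) and longer-term (throughout follow-up) efficacy". For the two percentage outcomes, "missing data will be considered missing (not impacting the denominator) in one analysis, and positive/not working in another". LDNS has one rule: "For LDNS, missing BrACs will be considered to break a string of negative samples". For the fourth outcome, "Time to job attainment will be evaluated with Cox survivor analyses, including covariates if needed". Self-report supplements the breath tests, "such that one can be considered drinking if either index is positive".

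The only Type I error rate is .05, under Power analyses. The Economic Evaluation section opens: "If primary aims are supported, we will conduct cost-effectiveness analyses". The Specific aims section, however, promises cost and cost-effectiveness estimates without any condition.

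Remote breath tests are scheduled in weeks 1-12 (Alcohol monitoring procedures, averaging 10 per week) and for 14 days at Month 12 (Compensation; Training in alcohol breath monitoring; the assessment table).

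**The concern.** Naming outcomes in advance fixes what is tested. It does not fix how two results become one verdict. Suppose LDNS is significant and % negative BrACs is not, or Month 3 is positive and the follow-up analysis is not. The plan does not say whether Aim 1 is then supported. If one positive outcome is enough, the aim's error rate is above the .05 that the plan states.

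The second problem is definition. LDNS and % negative BrACs are built from requested tests, and for about 38 weeks no remote tests are requested. The plan lets self-report mark someone as drinking, but not how self-report would form a longest run or a percentage of tests when none were due. This matters because Design considerations itself raises the criticism that benefits may fade once reinforcers end, and the longer-term drinking analysis should answer it.

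**Working it through.** **The plan's own figure.** Power analyses states 62 participants for d=0.47, alpha .05 and power .80. An exact two-sided t-test needs 73 per group, and 62 per group gives 73.8%, so the figure does not reproduce. That is a separate matter. The calculations below use the randomised numbers (70 per group, so 140 against 140 for each main effect) and do not depend on it.

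**False-positive chance within one aim.** Inputs: two outcomes, each tested two-sided at .05 (the plan does not state sidedness), with either counting as success. The correlation between the test statistics is assumed, because the documents give none.

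- Independent: 1 − (1 − 0.05)² = 1 − 0.9025 = 9.75%.
- Correlated: 1 − P(|Z1| ≤ 1.96 and |Z2| ≤ 1.96), bivariate normal.

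| Assumed correlation | 0 | 0.4 | 0.6 | 0.8 | 0.9 |
|---|---|---|---|---|---|
| At least one false positive | 9.75% | 9.3% | 8.75% | 7.8% | 7.0% |

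LDNS and % negative BrACs come from the same tests, so the lower end is more likely for Aim 1. If both outcomes must be significant, the chance that a null aim passes is at most 5%.

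**Cost of Holm.** The smaller p-value is tested at .025 and, if it passes, the other at .05. The worst step is therefore .025. Power is from the noncentral t with 2n − 2 degrees of freedom and noncentrality d√(n/2). For n=140 and d=0.47 that is 0.47 × √70 = 3.93, against critical values of 1.97 (.05) and 2.25 (.025).

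| Comparison | d | Power at .05 | Power at .025 |
|---|---|---|---|
| 140 vs 140 | 0.47 (planned) | 97.5% | 95.3% |
| 140 vs 140 | 0.30 (assumed) | 70.6% | 60.2% |
| 128 vs 128 | 0.47 (planned) | 96.3% | 93.3% |
| 128 vs 128 | 0.30 (assumed) | 66.7% | 55.8% |

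The 128 rows use the plan's 64 per group before its allowance for missing data. The table applies to the continuous outcomes only.

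**Breath-test coverage.** The unmonitored gap is 52 − 12 − 2 = 38 weeks. At 10 tests per week (stated for weeks 1-12; assumed for Month 12, where the procedures are described as similar), expected tests are 10 × 12 = 120 on treatment and 10 × 2 = 20 at Month 12. A measure combining the two windows would be 120/140 = 86% on-treatment.

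**The case against.** **Both outcomes may be meant.** Aim 2 joins its two outcomes with an 'and', which can be read as requiring both, and then nothing is inflated. That reading is possible, but no decision rule states it, and the Aim 1 sentence only says that differences in its two outcomes will be evaluated.

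**A much larger error rate is tempting.** A reader might multiply outcomes by horizons by missing-data rules and reach well above 10%. The documents do not support that. The two missing-data rules are offered as a range, which is a sensitivity purpose, and the plan never says that a win at any horizon or under any rule would count. What stands is that neither a lead rule nor a deciding horizon is named.

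**Pooling is not proposed.** A reader might infer that the two breath-test windows will be merged. The plan does not say so, and the assessment table lists the Month-12 block separately. Nor is the gap empty: TLFB covers the time since the last interview, and breath and urine samples are scheduled at the follow-up visits, with office breath tests not collected during the COVID-19 outbreak. These do not define LDNS or % negative BrACs across the gap, and that narrower point stands.

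**The economic analysis is not left without a basis.** Specific aims commits to it regardless. The condition in Economic Evaluation conflicts with that commitment, so the two passages need reconciling.

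**Censoring.** The absence of a censoring time for the Cox model is minor. Follow-up lasts one year, and censoring at the last interview or Month 12 is the usual default.

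**Conclusion.** The concern holds as a gap in the decision rule and in one outcome definition. Within Aim 1 or Aim 2 the false-positive chance is about 7% to 10%, rather than 5%, if each outcome is tested at .05 and either suffices. The figure rests on that either-outcome reading, two-sided tests and an assumed correlation. It is nearer the lower end for Aim 1, and there is no inflation if both outcomes are required. The inflation is modest, but the rule should be fixed before outcomes are seen.

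The longer-term versions of LDNS and % negative BrACs are undefined. A combined measure would be about 86% on-treatment and could not show whether benefit lasts after prizes stop, although the plan does not state that it will combine the windows.

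**What to change.** 1. Treat Aims 1 and 2 as separate families and apply Holm across each aim's two primary outcomes. State that error across aims is not controlled.
2. Name one deciding horizon per aim, for example weeks 1-12 for drinking and randomisation to Month 12 for employment. Report the other horizon as secondary. For time to job, write down the censoring rule (last employment interview or Month 12).
3. Name one of the two missing-data rules as the lead analysis for the percentage outcomes, with the other as its bound.
4. For longer-term drinking, analyse the Month-12 14-day breath-test window separately from weeks 1-12, and use TLFB drinking days for Months 4-12. Do not compute LDNS across the unmonitored gap.
5. Reconcile the unconditional cost-effectiveness commitment in Specific aims with the condition in Economic Evaluation.

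Requiring both outcomes is a valid alternative to Holm and needs no adjustment. If the outcomes were independent and shared the same effect, its power would be 0.9749² = 95.0% at d=0.47 but 0.7059² = 49.8% at an assumed d=0.30.

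**Cost.** SAP wording and no new data. For the continuous main effects, Holm's strictest step costs about 2 points of power at the planned effect (97.5% to 95.3%) and about 10 points at the assumed d=0.30 (70.6% to 60.2%). The cost for time to job cannot be worked out, because the documents give no hazard ratio or 12-month event count. The Month-12 window has about 20 expected tests per person against 120 in weeks 1-12, so it is less precise.

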Interventions for Unemployed Hazardous Drinkers

NCT02559609

Protocol V. 6/21

PROTOCOL: Interventions for unemployed hazardous drinkers

PRINCIPAL INVESTIGATORS: [name], and [name]

Despite recent improvements in the US economy, unemployment remains a significant concern, and estimates indicate that one-third of unemployed persons drink at hazardous levels, adversely impacting their health and abilities to find jobs. Reinforcement interventions are highly efficacious in reducing substance use, and they can be applied to increase job-seeking activities as well. In partnership with CT United Labor Agency, this project is designed to reduce hazardous drinking and enhance active participation in job-seeking activities among those with job loss. It will evaluate the independent and combined effects of reinforcing negative breathalyzer samples and job-seeking activities to ascertain the simplest and most cost-effective approach to improving outcomes in this population. Unemployed individuals with hazardous drinking ($N = 280$) will be randomly assigned to one of four conditions using a 2×2 design: standard care, standard care with reinforcement for submitting negative breathalyzer samples, standard care with reinforcement for job-seeking activities, or standard care plus reinforcement for both negative breathalyzer samples and job-seeking activities. Participants in all conditions will receive usual services part of CT United Labor Agency, along with a novel remote breath alcohol monitoring procedure. The study interventions will be in effect for three months, and participants will be followed for one year. Alcohol and other drug use, employment, psychiatric symptoms, and global measures of health will be assessed throughout treatment and follow-up. Reinforcing negative breathalyzer samples is expected to significantly reduce drinking, and reinforcing job-seeking activities is expected to increase re-employment rates and reduce time until job attainment. Reinforcing both negative breathalyzer samples and job-seeking activities is hypothesized to improve outcomes along both domains. The reinforcement interventions may also decrease psychiatric distress and slow progression of physical decline, common among the unemployed. If efficacious and cost-effective, results from this study may stimulate adoption of reinforcement interventions in the context of unemployment services. Reducing the adverse consequences of hazardous drinking and improving job re-entry may have pronounced benefits in a highly vulnerable segment of the US population.

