Inclusion criteria are: (1) age 18-65 years; (2) not worked for pay in the formal economy for >4 weeks; (3) willing to participate in a workforce training program and willing to accept either part-time or full-time work; (4) hazardous alcohol use defined by AUDIT scores ≥ 8 (Saunders et al., 1993), a mean of ≥ 2 drinks/drinking day or ≥ 14 drinks/week in men (≥ 1 drink/drinking day or >7 drinks/week in women) in the past 2 months, or submission of an alcohol positive breathalyzer (≥ 0.02 g/dl) or EtG positive urine sample; (5) English or Spanish speaking and able to read at 5th grade level; (6) have a valid photo ID; (7) willing and able to use study equipment (see below) and sign an off-campus property transfer form. See Human Subjects for rationale of criteria.

Exclusion criteria are: (1) have begun receiving unemployment benefits within the past 4 weeks; (2) worked full- or part-time <3 months in the past 3 years in the formal or informal (i.e., under-the-table) economy; (3) physiological alcohol withdrawal symptoms (score ≥ 10 on Clinical Institute Withdrawal Assessment for Alcohol-revised; Sullivan et al, 1989); (4) physiological withdrawal symptoms from an illicit drug use disorder; (5) serious untreated psychiatric illness (e.g., schizophrenia, bipolar disorder, or suicide risk); or (6) in recovery from gambling disorder ([name] et al, 2006a). See Human Subjects.

Screening procedure: Subjects will be screened using a form that assesses initial eligibility for two studies. Both studies are employment studies with similar inclusion/exclusion criteria. This study serves who are hazardous drinkers while the other study serves persons living with HIV/AIDS (PLWHA). If the subject is initially qualified for both studies on the basis of the screen, they will be offered the study that can best accommodate an additional active participant.

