With 70 participants/group in a 2x2 design, we will be overpowered to detect main effects of reinforcing negative BrACs on alcohol outcomes, and main effects of reinforcing job-related activities on employment outcomes. Nevertheless, this sample size provides power to ascertain if the combined reinforcement intervention is most effective. It also allows detection of a small to medium effect size in determining if reinforcing one behavior can improve both alcohol and employment outcomes (e.g., Group B > A, and Group C > A) to isolate the simplest efficacious reinforcement approach. Moreover, it permits evaluation of secondary outcomes and exploratory analyses of moderators and mediation effects.

Secondary aims are to evaluate the impact of interventions on other drug use, and mental and physical health indices. These are continuous measures, with missing data likely. If no systematic differences in missing data are noted, hierarchical linear models (HLM; Gibbons et al., 1993) using MIXREG (Hedeker, 1993) will analyze differences between groups over time. These analyses have advantages over repeated measures ANOVA as they estimate missing data via model parameter estimates and use real time, rather than scheduled time, of assessments. The same contrasts outlined above will be used to evaluate the aims. Analyses will be conducted for both short-term (e.g., BL to M3, with up to 3 data points/participant: BL,M1,M3) and long-term effects (BL through M12, with up to 6 data points: BL,M1,3,6,9,12). Models will include factors for group (using contrasts above), time, and interaction of group by time. Analyses will ascertain whether the interventions impact areas of functioning beyond alcohol use and employment indices. For example, reinforcement interventions can reduce psychiatric symptoms and improve quality of life ([name] et al., 2007b, in press c).

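### The two missing-data rules for the longer-term % days worked analysis can err on the same side when terminal loss differs between the Aim 2 groups, so they need not give the range they are meant to show

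*Combined protocol and SAP*

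**What the plan says.** The Data Analysis section names four primary outcomes, one of which is percentage of days worked for pay. On the model it says "ANOVAs (or ANCOVAs) will be conducted for drinking data and % days employed", in two windows: "evaluating both short-term (BL to month 3) and longer-term (throughout follow-up) efficacy". The abstract states that "participants will be followed for one year", so the longer window reaches Month 12.

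Two rules cover missing time. The first is "For % negative BrACs and % days working, missing data will be considered missing (not impacting the denominator) in one analysis"; the second is "and positive/not working in another to consider the range of possibilities". The population statement is "All randomized participants will be included using intent-to-treat analyses". The section does not standardise the observed window, require a minimum observed period, or add a third analysis for this outcome.

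Two other places matter. Inclusion criterion 2 requires that a participant has "not worked for pay in the formal economy for >4 weeks". For secondary outcomes, the plan specifies hierarchical linear models that use actual assessment time, and says of them: "These analyses have advantages over repeated measures ANOVA as they estimate missing data via model parameter estimates".

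**The concern.** An outcome that starts near zero and rises has a lower average over its first three months than over twelve. Dropping unobserved time from the denominator therefore does not leave a person's value neutral. It replaces a full-year percentage with an early one, and the ANOVA cannot tell the two apart. Scoring the missing time as not working lowers the value again.

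The two rules are presented as covering the range of possibilities. If both fall below the true level in the arm that loses more people, the true contrast can lie outside the pair, and agreement between the two analyses would reassure falsely. This affects the longer-term test of Aim 2 on one of its two primary employment outcomes.

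**Working it through.** The documents give no figure for the level or trajectory of percentage worked, or for bias from these rules, so there is nothing of the plan's own to reproduce. The calculation below is an illustration.

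**Inputs**
- Job attainment of 28% v 50%, from the veterans' vocational trial in Preliminary studies. Treating this as attainment by 16 weeks, the length of that intervention, is an assumption.
- Assumed: exponential time to job, jobs kept, 5 of 7 days worked once employed, and loss unrelated to employment at Month 3 (week 13 of 52).
- The two rules, from the Data Analysis section.

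**Formulas**
- Weekly rate: λ = −ln(1 − p)/16. This gives 0.0205 (28%) and 0.0433 (50%).
- Mean percentage worked over weeks 0 to t: A(t) = (500/7) × [1 − (1 − e^(−λt))/(λt)].
- A lost person's value is A(13) under rule 1 and A(13) × 13/52 under rule 2.
- Arm mean with a fraction q lost: (1 − q) × A(52) + q × (lost person's value).

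**Level per person**

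| | 28% rate | 50% rate |
|---|---|---|
| Full year, A(52) | 27.5 | 43.1 |
| Lost at Month 3, rule 1 | 8.7 | 16.8 |
| Lost at Month 3, rule 2 | 2.2 | 4.2 |

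Both rules lie below the full-year value in both columns. The true difference is 15.5 points (43.05 − 27.53).

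**Contrast (reinforced minus control)**

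| Loss, control / reinforced | Rule 1 | Rule 2 |
|---|---|---|
| 6% / 6% | 15.1 | 14.7 |
| 5% / 15% | 12.5 | 11.0 |
| 15% / 5% | 17.0 | 17.4 |

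Worked case, 5%/15%, rule 1: (0.85 × 43.05 + 0.15 × 16.81) − (0.95 × 27.53 + 0.05 × 8.74) = 39.12 − 26.59 = 12.5. With loss at Month 6 instead, the same pattern gives 13.9 and 12.2.

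**No true effect, 10-point gap in loss, both arms at the 28% rate.** The spurious difference is 0.10 × (27.5 − 8.7) = 1.9 points under rule 1 and 0.10 × (27.5 − 2.2) = 2.5 under rule 2.

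**Scale.** The model's standard deviations are about 26 and 23. With 140 per side, the standard error is √((26² + 23²)/140) ≈ 2.9 points. The error at 6% balanced loss (0.4 to 0.8 points) is about 0.15 to 0.28 of a standard error. At 5% v 15% it is 3.0 to 4.6 points, or about 1.0 to 1.6 standard errors.

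**Changing the trajectory.** Suppose the reinforced arm returns to the control job-finding rate after week 12, when reinforcement ends.
- 6% loss per arm at week 26, jobs kept: true 8.77, rules 8.83 and 8.53. The pair brackets the truth.
- 6% loss per arm at week 13, 2% weekly job loss: true 6.24, rules 6.31 and 5.97. Again bracketed.
- The second case with 5%/15% loss: 5.1 and 3.7, both too small. Reversed: 7.6 and 7.9, both too large.

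The same-side error under unequal loss therefore survives the change of trajectory, but the shrinkage under balanced loss does not.

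**The case against.** The strongest reply is that the problem needs unequal terminal loss, and the documents give little reason to expect it. Data Quality Control reports under 6% lost completely in the team's earlier studies and no group differences in missing data where compensation was adequate, and it commits to checking for group differences here. Every arm receives the same follow-up payments. This stands as an argument about size. It does not remove the point: the 6% covers complete loss only, no figure is given for people who stop partway, and no action is specified if loss differs.

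A reader might infer that prize arms will be retained better. The documents do not support this. Prizes end at week 12, before most of the longer-term loss could occur, and Group B also draws prizes while sitting on the control side of the Aim 2 contrast. The direction of any imbalance is unknown.

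The premises can also be questioned. Entry bars formal work only, whereas the outcome is work for pay. No trajectory is given. If work falls later, rule 1 can overstate: in one falling scenario with 20% lost at Month 6, the true level was 10.6, rule 1 gave 11.4 and rule 2 gave 10.0. The longer-term outcome is not expressly defined as one 12-month percentage per person, although a denominator rule suggests it. If employment is asked back to the last interview, a returning participant fills the gap and only terminal loss matters. These are fair limits.

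It would also be wrong to say that the plan models employment over time nowhere. It includes a latent growth model of days employed with treatment as a predictor, but as a step in the mediation analysis. Time to job attainment, a co-primary outcome, is analysed by Cox regression, which can censor at last contact. Neither gives the longer-term contrast in percentage worked.

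**Conclusion.** The point holds conditionally and is minor. If work rises over the year, both rules understate the level in any arm with terminal loss. When that loss differs between the Aim 2 sides, both can then move the contrast the same way: in the illustration, 19% to 29% too small with 5% v 15% loss, and 10% to 12% too large when reversed. The pair then does not give the intended range. These sizes rest on the assumed job-finding rates, jobs being kept and loss at Month 3.

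A reader might go further and conclude that the contrast is attenuated even when loss is balanced. That is not general. It follows from letting the effect on job-finding run for the whole year, and the rules can bracket the true contrast if the effect stops at week 12. Near the documented loss rate, the error under balance is a small fraction of a standard error.

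**What to change.** For the longer-term analysis:
- Compute percentage of days worked for each interview interval, ending at Months 1, 3, 6, 9 and 12.
- Fit a mixed model with the Aim 2 contrast, time as a categorical factor, and their interaction. Linear time would misfit a plateau.
- Use robust or bootstrap standard errors, because many interval values will be zero.
- Report the length-weighted 12-month difference as the result, and keep the two ANOVA versions as supportive analyses.
- State that this model runs whether or not missingness differs between groups. The secondary-outcome models are conditional on finding no systematic differences in missing data. Carrying that condition over would remove the analysis in the case where it is needed.

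In simulation under the same job-finding assumptions, a normal-likelihood estimate from the observed intervals recovered the true difference to within 0.01 in the three loss patterns tabulated. With 30% loss among unemployed reinforced participants and 10% elsewhere, it gave about 16.0 against a true 15.5, while the planned rules gave about 11.7 and 11.1.

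The cost is plan wording and one more model; no new visits are needed. It relies on missing at random given observed employment, and it cannot help for someone with no interval observed after baseline.
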